### 6.4 Data Presentations

The data will be summarised in tabular form by treatment group apart from disposition of subjects, prior and concomitant medications and background and demographic data which will be summarised by treatment group and overall subjects.

Treatment groups will be presented in the following order using these labels:

- SoC + C21 100 mg b.i.d
- SoC + Placebo

Listings will be sorted by treatment group, site and subject number and date/time of assessment.

Data will be summarised and listed using the following analysis sets:

	Enrolled	RAS	FAS	PPAS	SAS
Tables	
 
• Disposition
 
	
 
• Withdrawal
 
	
 
• Demography
 
• Efficacy
 
	
 
• Demography
 
• Efficacy (primary endpoint only)
 
	
 
• Demography
 
• Prior and concomitant medications
 
• Medical history
 
• Exposure
 
• Safety
 

Listings	
 
• Completion/ withdrawal
 
• Eligibility
 
	
 
• Protocol deviations
 
• Analysis sets
 
• Demography
 
• Medical history
 
• Disease under investigation
 
• Hospitalisation
 
• Visit dates
 
• Randomisation
 
• Efficacy
 
• Biomarkers
 
			
 
• Prior and concomitant medications
 
• Safety
 
• IMP administration
 
• Exposure
 

1. Demography will be summarised using the FAS and repeated for the PPAS and SAS where the analysis sets differ for at least 1 subject. If either of these analysis sets are identical to the FAS the summary will not be presented.

Only scheduled post baseline data will be tabulated, post-baseline repeat/unscheduled assessments will not be included in tables, although they will be listed and in particular all clinically significant values will be noted.

## 6.5 Disposition of Subjects

The number and percentage of all subjects enrolled, included in the RAS, FAS, PPAS and SAS, who completed study treatment and prematurely discontinued study treatment, who completed the study and prematurely discontinued the study and study duration will be summarised. The number and percentage of subjects will be summarised by their reasons for withdrawal from treatment and the study.

Study duration will be derived as the number of days between date of randomisation and the date of study completion or the date of early study withdrawal. The timing of withdrawals will be explored using the RAS. Time to withdrawal from study treatment will be calculated in hours as (Date and time of withdrawal from treatment) – (Date and time of informed consent). For subjects not withdrawing from treatment, time to withdrawal will be censored at the time of their last study treatment administration. The time to withdrawal will also be presented graphically using a Kaplan Meier (KM) plot. KM estimates for the 25th, 50th and 75th percentiles of time to withdrawal will also be presented.

Eligibility for each of the analysis sets along with reasons for exclusion will be listed. Inclusion and exclusion criteria failures will be listed. Study completion/withdrawal data will be listed.

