## 6.3 Analysis Sets

The **Enrolled Set** includes all subjects who provide informed consent irrespective of whether they received the study treatment.

The **Randomised Analysis Set (RAS)** includes all subjects who have been randomised, irrespective of whether they received the study treatment.

The **Full Analysis Set (FAS)** will consist of all subjects who have been randomised and received at least one dose of IMP and who have at least one post-baseline assessment of efficacy. A post-baseline assessment of efficacy includes an assessment of any of the parameters detailed in Section 6.10 of this SAP. Subjects will be analysed according to the treatment they are assigned to at randomisation, irrespective of what treatment they actually received.

The **Per-Protocol Analysis Set (PPAS)** will be a subset of the FAS and consist of all subjects without any major protocol deviations that are judged to compromise the analysis of the data. All protocol deviations will be judged as major or minor prior to database lock.

The **Safety Analysis Set (SAS)** consists of all subjects who have received at least one dose of IMP. Subjects will be analysed according to the treatment actually taken.

The list of subjects included in the PPAS will be agreed prior to breaking the blind once all study data is available. The definitions for the enrolled set, RAS, FAS and SAS are sufficient to determine the subjects included within these analysis sets and so do not require listing and agreeing prior to breaking the blind.

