#### **6.10.2.4 Time to Need of Mechanical Invasive or Non-Invasive Ventilation**

Time to need of mechanical ventilation (invasive or non-invasive) for each subject is calculated in hours as (Date and time of decision for need of ventilation) – (Date and time of first administration of study treatment). The treatment period for each subject is from the date and time of their first study treatment administration to the date and time of their last study treatment administration + 12 hours. For subjects who withdraw from treatment with the reason for withdrawal as need for mechanical invasive or non-invasive ventilation, the date and time of decision for need of ventilation is taken from the date and time at which the subject withdrew from treatment (as recorded on the End of Treatment page of the eCRF). For subjects who do not withdraw from treatment due to need for mechanical invasive or non-invasive ventilation but who have an entry on the Mechanical Ventilation eCRF page indicating that ventilation was required during the treatment period, the start date and time from this page will be used to calculate time to need of ventilation. For subjects who do not record a need for ventilation but die during the treatment period, the date and time of death as recorded on the Adverse Event page will be used to calculate the time to need of ventilation.

For subjects not requiring ventilation during their treatment period and who do not die during the treatment period, the time to need of mechanical ventilation will be right censored at the date and time of treatment completion + 12 hours. For subjects who withdraw from treatment for reasons other than need for ventilation or death, the time to need of ventilation will be right censored at the date and time of withdrawal from treatment + 12 hours. The date and time of last treatment administration + 12 hours is a censoring event, should a subject be assessed as having need for ventilation after this time it will be disregarded in the analysis.

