6.5 Schedule of Events

6.5.1 Screening (Visit 1)

Prior to and no later than at start of screening (Visit 1), i.e. before any trial-related activity takes place, the Investigator or a qualified designee will explain the nature of the trial, its purpose, the procedures involved, the expected duration, the potential risks and benefits involved, and any discomfort the subject may entail. All explanations shall be in layman's language. The subject will be provided with a copy of the information sheet. The subject must be given sufficient time to consider the trial before deciding whether to participate.

After signed informed consent is obtained from the subject, the screening procedures can be initiated.

All subjects giving informed consent to participate in the trial will receive a screening number. During the screening visit, the subject is evaluated for eligibility (see Section 5.1 and 5.2).

The following procedures are performed:

- Written informed consent to be obtained
- Assignment of screening number
- Check of in- & exclusion criteria
- Assessment of eligibility which includes review of demographics, medical history, concomitant illnesses and medication, physical examination, height, body weight, and measurement of blood pressure, pulse, respiration rate, and body temperature (morning values)
- Medical history and concomitant medication
- 12-lead electrocardiography (ECG)
- Recording need of supplementary O₂
- Blood sampling for:
 - o CRP
 - o HBsAG, HCVab, HIV 1+2 Ag/Ab (see Table 2 and Section 8)
 - Safety (haematology and biochemistry) (see Section 8.2.7)
- Urinalysis (dipstick) for bilirubin, glucose, ketones, protein, specific gravity, urobilinogen, pH (see Section 8.2.7)
- Pregnancy testing (urine dipstick), if positive a blood pregnancy test must be performed to confirm positive pregnancy
- Adverse events

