6.5.2 Treatment Period (Visits 2-8)

The treatment period lasts for 7 days (Visit 2-8). The procedures to be performed at each visit are specified below.

Vicore Pharma AB Version: 2.0 Trial ID: VP-C21-006 Date: 14-Aug-2020

Visit 2

Visit 2 can be scheduled as soon as the relevant screening assessments are available. Visit 2 must occur within 3 days from Visit 1 (screening).

The following procedures are performed:

- Re-evaluation of in- & exclusion criteria
- Short physical examination (including vital signs)
- Evaluation of ECG and laboratory results from Visit 1
- Assignment of randomisation number
- Concomitant medication
- Recording need of supplementary O₂
- Blood sampling for:
 - o CRP
 - Safety (haematology and biochemistry) (see Section 8.2.7)
 - o IL-6, IL-10, TNF, CA125, ferritin
 - o Biomarkers
- Urinalysis (dipstick for bilirubin, glucose, ketones, protein, specific gravity, urobilinogen and pH)
- IMP administration twice daily including diatery restrictions (see Section 5.3.2)
- Check of withdrawal criteria
- Adverse events

Visits 3-8

- Concomitant medication
- Short physical examination (including vital signs at the judgement of the Investigator)
- Recording need of supplementary O₂
- Blood sampling for
 - o CRP
 - o Safety (haematology and biochemistry) (see Section 8.2.7)
 - o IL-6, IL-10, TNF, CA125, ferritin
- Urinalysis (dipstick for bilirubin, glucose, ketones, protein, specific gravity, urobilinogen and pH)
- IMP administration twice daily including dietary restrictions (see Section 5.3.2)
- Check of withdrawal criteria
- Adverse events

In addition for Visit 8 (end-of-treatment) only:

- Pregnancy testing (urine dip-stick), if positive a blood pregnancy test must be performed to confirm positive pregnancy
- Biomarkers
- Drug accountability

Vicore Pharma AB Version: 2.0 Trial ID: VP-C21-006 Date: 14-Aug-2020

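### Time to withdrawal from study treatment is counted from informed consent, so the Kaplan–Meier summary includes a screening gap in which no withdrawal can occur, and some randomised, never-dosed subjects have no defined time

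*SAP*

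**What the plan says.** SAP Section 6.5 gives the quantity as "calculated in hours as (Date and time of withdrawal from treatment) – (Date and time of informed consent". For everyone else, "For subjects not withdrawing from treatment, time to withdrawal will be censored at the time of their last study treatment administration". The population is stated directly: "The timing of withdrawals will be explored using the RAS". SAP Section 6.3 defines that set as one that "includes all subjects who have been randomised, irrespective of whether they received the study treatment". The planned output is a Kaplan–Meier plot with the 25th, 50th and 75th percentiles. No test is planned.

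On timing, protocol Section 6.5.1 states: "After signed informed consent is obtained from the subject, the screening procedures can be initiated". Protocol Section 6.5.2 adds: "Visit 2 must occur within 3 days from Visit 1 (screening". Table 1 of the protocol gives the Visit 2 window as 1–3 days and places both randomisation and the first IMP administration at that visit.

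Other timings in the SAP use a later origin. Time to need of ventilation (6.10.2.4) is counted from "Date and time of first administration of study treatment". Study day (6.2.2), treatment duration (6.9) and the AE onset times in the listings (6.11.1) also start at first dose. Study duration, in Section 6.5 itself, starts at randomisation.

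**The concern.** The event is stopping study treatment, but the clock starts before treatment is possible. Membership of the RAS requires randomisation, so every subject on the curve is event-free from consent to Visit 2 by construction. The length of that stretch differs between subjects and reflects screening logistics, not tolerance of treatment or course of disease.

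The output is likely to be read. Protocol Section 5.4.1 makes discharge a reason for withdrawal from IMP, and Section 3.8 expects these patients to be discharged or in intensive care within 7 days. Early stopping may therefore be common enough for some percentiles to be reached. A reader who takes the reported median as time from the start of treatment would take a figure that is too long.

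There are also two practical gaps. A result in hours needs a time of consent. And the censoring rule relies on a last administration, which a never-dosed subject does not have.

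**Working it through.** The documents state no figure for time to withdrawal, so there is none to reproduce. The check is of the definition and of how far the origin moves the output.

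**Inputs**
- Consent to first dose: about 24–72 h, from the 1–3 day window in protocol Table 1. This is approximate. Afternoon consent followed by a next-morning dose is under 24 h, and consent obtained ahead of Visit 1 lengthens the gap.
- Full course: 14 doses (SAP 6.9). Assuming 12-hourly dosing, the last dose falls 13 × 12 = 156 h after the first.
- Share of subjects withdrawing: not given; 15% to 80% assumed.

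**Censoring times of completers, counted from consent**
- Short gap: 156 + 24 = 180 h, of which the gap is 24/180 = 13%.
- Long gap: 156 + 72 = 228 h, of which the gap is 72/228 = 32%.

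After about 180 h the subjects still at risk are increasingly those with long screening, so the tail of the curve partly describes screening length.

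**Effect on the percentiles**

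Withdrawal times were simulated as exponential with rate −ln(1 − f)/156, where f is the share withdrawing by 156 h, and censored at 156 h after first dose (400,000 subjects). Times are in hours.

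| f (assumed) | Percentile | From first dose | From consent, gap 24 h | From consent, gap 72 h | From consent, gap uniform 24–72 h |
|---|---|---|---|---|---|
| 15% | all three | not reached | not reached | not reached | not reached |
| 30% | 25th | 125.9 | 149.9 | 197.9 | 174.0 |
| 60% | 25th | 49.0 | 73.0 | 121.0 | 97.6 |
| 60% | 50th | 118.0 | 142.0 | 190.0 | 166.4 |
| 80% | 25th | 27.9 | 51.9 | 99.9 | 77.0 |
| 80% | 50th | 67.3 | 91.3 | 139.3 | 116.3 |
| 80% | 75th | 134.8 | 158.8 | 206.8 | 183.8 |

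Percentiles not shown for 30% and 60% are not reached. Each percentile that is reached moves later by the gap: 24 h, 72 h, or 48–49 h when the gap is uniform.

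**Whether the formula can be computed**
- SAP 6.7.1 lists the informed consent date, and protocol Section 11.2 names only dates of consent as source data. The same section does name the date and time of IMP administration.
- A never-dosed RAS subject with a recorded withdrawal date and time is an event and can be placed. One without a recorded withdrawal has no last administration to be censored at. SAP 6.10.2.3 assures an End of Treatment page only for subjects who start treatment, so a withdrawal time may also be absent. The documents give no count of such subjects; each is 1/75 = 1.3% of an arm.

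**The case against.** The strongest reply is that the SAP states its origin openly, and a Kaplan–Meier curve of time from consent is a valid estimate of time from consent. A reader might infer that the estimates are wrong; that does not follow. They answer a less useful question than the one suggested by the phrase withdrawal from study treatment. Time on treatment is in any case available elsewhere: SAP 6.9 summarises treatment duration, actual treatment duration and exposure, anchored at first dose. This stands, and it limits how much the issue matters.

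A reader might also infer a bias between the arms. The documents do not support that: the gap closes at Visit 2, where randomisation takes place, so it should be similar in both arms.

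A third inference is that the primary result is affected because early leavers' CRP values are carried forward. SAP 6.10.1 builds that endpoint from CRP assessments relative to the final administration, and time to withdrawal is not an input. It is context only.

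On size, it is tempting to set 24–72 h against a 168-hour course and report 14–43% inflation for every subject. That treats a visit window as exact hours and uses a span that is not the one censored, since censoring is at the last dose.

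On never-dosed subjects, only those with no recorded withdrawal lack a time. They should be few, because randomisation and first dose share a visit.

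What remains is an origin out of line with the other SAP timings cited, given without a reason, and a rule that is incomplete at its edges.

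**Conclusion.** The point holds as a minor one. The planned curve and any percentile that is reached are later than time from treatment start by the screening gap, roughly 1–3 days against a dosing span of about 156 h. The tail partly reflects differences in screening length. The size rests on the Table 1 window, on 12-hourly dosing and on assumed withdrawal shares; at 15% withdrawing no percentile is reached under either origin and only the curve moves.

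The need for a consent time is a gap in what the documents show, since the eCRF itself may collect one. The missing censoring rule is a real omission, but for a narrow group. The output is descriptive, and no test, sample size, efficacy result or safety result depends on it.

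**What to change.** In SAP 6.5, define time to withdrawal as date and time of withdrawal from treatment minus date and time of first administration, in RAS subjects who received at least one dose, by randomised arm. Keep the existing censoring rule, which is then defined for everyone on the curve, and report randomised, never-dosed subjects as a separate count. This also removes the need for a consent time.

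Moving the analysis to the Safety Analysis Set is not the right shortcut. That set groups subjects by treatment actually taken (SAP 6.3) and admits dosed subjects irrespective of randomisation (SAP 6.12), whereas this is a disposition summary that SAP 6.4 assigns to the RAS.

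An acceptable alternative is to keep the full RAS, start at randomisation and state one rule for never-dosed subjects. SAP Section 4 mentions only a date of randomisation, so that version needs a recorded time or a result in days.

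The cost is a small edit to the SAP text, a note to the analysis-set table in 6.4 and one changed derivation. No new data are needed for the first option.

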## 6.6 Protocol Deviations

A Protocol Deviation Criteria (PDC) form has been utilised to define the following for any expected protocol deviations:

- Protocol deviation source (either obtained from the database, programmatically and/or via clinical review),
- Protocol deviation category,
- Classification (major/minor),
- Resulting inclusion or exclusion from analysis sets.

This form has been reviewed and approved by Vicore Pharma AB prior to commencing collection of protocol deviations.

All protocol deviations will be assessed and documented on a case-by-case basis. A review of all captured deviations will be completed by Vicore Pharma AB prior to database lock and major deviations considered to compromise the efficacy results will lead to the relevant subject being excluded from the PPAS.

Details of all protocol deviations (date, deviation category, specific details, action taken and classification of major or minor) will be listed. The listing will also include whether a subject was excluded from the PPAS.

## **6.7 Background and Demographic Characteristics**

### **6.7.1 Demography**

Demographic characteristics (age, sex, ethnic origin and race), body measurements (height, weight and body mass index (BMI)) collected at Screening will be summarised. Age ( $\leq$ median age at baseline,  $>$ median age at baseline), supplemental oxygen use at baseline and CRP value at baseline ( $\leq$ median value at baseline (mg/l),  $>$ median value at baseline (mg/l)) will also be presented to align with the subgroup analyses discussed in Section 6.10.6 of this SAP.

Age will be reported using the values entered into the eCRF.

BMI will be calculated as (weight (kg)/height (m)) using the measurements provided at Screening.

All subject demographic data will be listed including informed consent date and the protocol version enrolled under.

### **6.7.2 Medical History**

Medical history events will be coded using the latest Medical Dictionary for Regulatory Activities (MedDRA) dictionary version. The version used will be indicated in the data summaries and listings. The number and percentage of subjects will be presented for ongoing conditions and previous conditions separately by system organ class (SOC), and preferred term (PT), where SOC and PT will be presented in decreasing frequency of the total number of subjects with medical history events. All events will be listed.

### **6.7.3 Hospitalisation**

The date of admission to hospital and the date of discharge from hospital will be listed. The duration of hospital stay will be derived in days as date of the discharge - date of admission + 1.

### **6.7.4 Disease Under Investigation**

The date of confirmed coronavirus infection diagnosis will be listed. The time from diagnosis to treatment, calculated in days as date of first study treatment administration – date of diagnosis, will also be listed.

## **6.8 Prior and Concomitant Medications**

Medications will be coded using the latest World Health Organization Drug dictionary (WHO Drug) version. The version used will be indicated in the data summaries and listings.

Prior medications are defined as those that started and ended prior to first administration of study treatment. Any medications started on or after first administration of study treatment will be deemed to be concomitant medications. Medications that started prior to first administration of study treatment and are ongoing at the first administration of study treatment will be considered as both prior and concomitant medications. If medication dates are incomplete and it is not clear whether the medication was concomitant, it will be assumed to be concomitant.

The number and percentage of subjects taking prior and concomitant medications will be summarised separately by medication class and standardised medication name, where medication class and standardised medication name will be presented in

decreasing frequency of the total number of subjects with medications. Medications which have started prior to first administration of study treatment and are ongoing at the first administration of study treatment will be included in both the summary of prior medications and the summary of the concomitant medications. In summary tables, subjects taking multiple medications in the same medication class or having the same standardised medication recorded multiple times in the study will be counted only once for that specific medication class and standardised medication name.

Medication data will be listed, where concomitant medications will be flagged.

## **6.9 Administration of Study Treatment and Exposure**

For each treatment administration at each visit, the dose administered will be summarised. Dose will be calculated as the number of capsules consumed\*50 mg.

The total number of doses of study treatment administered, the treatment duration, actual treatment duration and exposure will be summarised.

Treatment duration will be derived in days as date of the last administration of study treatment - date of first administration of study treatment +1.

Actual treatment duration will be derived as the number of days a subject received study treatment during the treatment period, calculated as treatment duration – number of days of missing administration. Where a subject missed one of the two administrations on a day, they will still be considered to have been treated on that day for this calculation.

Exposure will be calculated as (actual number of doses received/expected number of doses)\*100. The expected number of doses will be calculated as treatment duration\*2. For example, should a subject complete treatment, the expected number of doses is 14.

Details of the timings of treatment administration, the number of capsules administered and reasons for doses not taken will be listed along with the fasting information confirming that the subject completed the required fasting periods both prior to and following study treatment administration. The treatment duration, actual treatment duration and exposure information will be also listed.

